7.2 Treatment Administration and Schedule

Subjects entering the study from RPC01-2201 will continue to receive ozanimod 0.92 mg/day (equivalent to ozanimod HCl 1 mg). Subjects entering the study from RPC01-3201, RPC01-3202, or RPC01-3203 will initiate ozanimod treatment in accordance with a 7-day dose escalation as follows:

- Days 1 through 4: Ozanimod 0.23 mg daily (equivalent to ozanimod HCl 0.25 mg)
- Days 5 through 7: Ozanimod 0.46 mg daily (equivalent to ozanimod HCl 0.5 mg) (administered as two 0.23-mg capsules)
- Day 8 through End of Study: Ozanimod 0.92 mg daily (equivalent to ozanimod HCl 1 mg)

[REDACTED] Subjects should be instructed to take IP at approximately the same time each day with or without food.

If subjects miss dosing for more than 14 days, they are required to complete the [REDACTED]

An overdose is any dose of IP given to a subject or taken by a subject that exceeds the dose described in the protocol. There is no information regarding overdose with ozanimod. Any overdose, with or without associated AEs, must be promptly reported to the Medical Monitor or other designated Drug Safety Center. The overdose should be recorded in the Overdose eCRF. Any AEs associated with an overdose should be reported on relevant AE/SAE sections in the eCRF.

Please refer to the Investigator's Brochure for more information.

7.2.1 *Instructions for Missed Doses*

Subjects should be instructed that if they forget to take a dose, they can take the dose within 4 hours of the normal dosing time. If the subject vomits the capsule, he/she should be instructed not to take another capsule on the same day, but to take the next dose at the regular time on the following day.

If a single dose is missed during the first 2 weeks of treatment, or for more than 7 consecutive days during Days 15 to 28, treatment must be reinitiated using the 7-day titration regimen (4 days of dosing at 0.23 mg daily [ozanimod HCl 0.25 mg] and 3 days of dosing at ozanimod 0.46 mg daily [ozanimod HCl 0.5 mg]). If a subject misses a dose during dose escalation, the Medical Monitor should be contacted to discuss completing the dose escalation schedule. The missed dose and extended days for escalation doses need to be documented as appropriate in the eCRFs.

If a subject misses more than 14 consecutive doses for any reason, the Medical Monitor must be contacted to discuss procedures for resuming therapy,

7.3 Method of Treatment Assignment

A single 0.92 mg oral daily dose of ozanimod will be administered.

7.4 Packaging and Labeling

Ozanimod capsules will be packaged in 30 cc white high-density polyethylene bottles (35 capsules per bottle, apart from the dose escalation kits), closed with a 28-mm child-resistant screw-cap that is induction sealed. The ozanimod 0.23 mg capsules will be bottled in a 12-count bottle, intended to supply the dose-escalation period only. The ozanimod 0.92 mg capsules will be bottled into a 35-count bottle, intended to supply daily treatment of the intended regimen following the dose-escalation period. To aid with visual identification of dosage strength, the cap on the 12-count dose-escalation bottles is blue, and the cap on the 35-count bottles is white.

The label(s) for IP will include sponsor name, address and telephone number, the protocol number, IP name, dosage form and strength (where applicable), amount of IP per container, lot number, expiry date (where applicable), medication identification/kit number, dosing instructions, storage conditions, and required caution statements and/or regulatory statements as applicable. Additional information may be included on the label as applicable per local regulations.

7.5 Investigational Product Accountability and Disposal

Investigational product should not be used for purposes other than as defined in this protocol.

All supplies of IP will be accounted for in accordance with GCP. There will be an individual IP accountability record for each subject and the Investigator should maintain accurate records of the disposition of all IP supplies received during the study. These records should include the amounts and dates that clinical drug supplies were received, dispensed to the subject, returned by the subject, and returned to the sponsor. If errors or damages in the clinical drug supply shipments occur, the Investigator should contact the Clinical Monitor immediately. Each Investigator will provide copies of the IP accountability records for inclusion in the Study Master File after database

lock. The Clinical Monitor will periodically check the supplies of IP held by the Investigator or pharmacist to verify accountability of all IP used.

The Investigator will provide the IP only to the identified subjects of this study, according to the procedures described in this study protocol. After the end of the study, the Clinical Monitor will perform final accountability, package, seal, and prepare for shipment. Investigational product and all medication containers will be returned to the clinical supply distribution vendor and documentation will be returned to the contract research organization (CRO). The CRO will verify that a final report of IP accountability is prepared and maintained in the Investigator's Trial Center File.

The sponsor (or designee) will review with the Investigator and relevant site personnel the process for IP return, disposal, and/or destruction including responsibilities for the site versus sponsor (or designee).

7.6 Investigational Product Compliance

It is the Investigator's responsibility to ensure that subjects are correctly instructed on how to take their IP, and that each subject is fully compliant with his/her assigned dosage regimen. Records of IP used and intervals between visits will be kept during the study. Drug accountability will be noted by the Clinical Monitor during site visits and at the completion of the study. Subjects will be asked to return all unused medication at the end of the study. The IP should be dispensed by the Investigator, or by a qualified individual under the Investigator's supervision.

Overall study noncompliance is defined as taking less than 80% or more than 120% of IP during the entire treatment period.

At each visit, previously dispensed IP capsules will be collected by the Investigator, or by a qualified individual under the Investigator's supervision, and compliance assessed. Subjects exhibiting poor compliance as assessed by medication counts (ie, 2 or more missed medication days in 1 week) and their response to a medication compliance question at each visit should be counseled on the importance of good compliance to the study dosing regimen. Subjects who are persistently noncompliant (< 80% or > 120%) should be discussed with the Medical Monitor to determine whether they should be withdrawn from the study.

8 CONCOMITANT MEDICATIONS AND PROCEDURES

All treatments, other than ozanimod, being taken by the subjects on entry into the study or at any time during the study, including through the [REDACTED] Safety Follow-up Visit, are regarded as concomitant treatments and must be documented on the appropriate section of the eCRF. Additionally, all diagnostic, therapeutic, or surgical procedures relating to CD should be recorded.

Administration of concomitant medications must be reported along with dosage information, dates of administration, and reasons for use. For medications with a single active ingredient, generic names for concomitant medication should be used if possible. For combination products, brand names should be used. The total daily dose should be filled in whenever possible.

[figure not shown]
8.1 Permitted Concomitant Medications and Procedures

Any medication that is considered necessary for the subject's health and that is not expected to interfere with the evaluation of or interact with IP may be continued during the study. All treatments being taken in addition to the IP by the subjects on entry to the study or at any time during the study are regarded as concomitant treatments and must be documented on the appropriate section of the eCRF. All prior medications that were continuing at the time of study discontinuation in the prior study or any new medications that started between the prior study discontinuation and enrollment in RPC01-3204 need to be documented.

The decision to temporarily interrupt dosing for treatment of an intercurrent medical condition, or for major surgery that could present an unreasonable risk to the subject, remains the responsibility of the treating physician, which will not be delayed or refused by the Sponsor. Prior to interruption of dosing, the Investigator may contact the Medical Monitor and forward appropriate supporting documents for review and discussion. The Investigator will report the action taken with IP. The Medical Monitor should be contacted to discuss treatment re-initiation ([Section 7.2.1](#)). See [Section 14](#) for permanent discontinuation of IP.

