1 INTRODUCTION

1.1 Disease Background

Crohn's disease (CD) is an immune-mediated inflammatory disease of the gastrointestinal (GI) tract. Annual incidence varies geographically, with estimates ranging from 3.1 to 14.6 per 100,000 people in the United States and from 0.1 to 16 per 100,000 worldwide ([Lakatos, 2006](#)). Subjects with CD suffer from diarrhea, rectal bleeding, weight loss, abdominal pain, and fever. CD is characterized by a lifelong chronic course of remissions and exacerbations. The pathology of this disease is characterized by transmural infiltration of lymphocytes and macrophages, granulomas, fissuring ulceration, and submucosal fibrosis. The transmural inflammatory process of CD predisposes subjects to the formation of fistulas and it has been estimated that approximately 35% of subjects will have at least 1 fistula during the course of their disease ([Schwartz, 2002](#)). In a recent study, within 10 years of diagnosis, 50% of adults with CD had undergone bowel surgery ([Peyrin-Biroulet, 2010](#)).

The current standard of medical care for patients with moderately to severely active CD consists of anti-inflammatory approaches, such as corticosteroids, azathioprine (AZA)/6-mercaptopurine (6-MP), methotrexate (MTX), and biologics such as anti-tumor necrosis factor (TNF) α , anti-interleukin (IL)-12/IL-23, or anti-integrins.

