6.3 Efficacy Assessments

See [Section 2](#) for a description of study endpoints.

6.3.1 *Crohn's Disease Activity Index*

The CDAI is a composite score that is used to measure the clinical activity of CD. The CDAI uses a questionnaire with responses scored numerically and weighted. Scores range from 0 to approximately 600, with higher scores indicating greater disease activity. The 8 components used to assess the CDAI and their weighting factors are noted in [Table 3](#). The definitions of mild, moderate, and severe CD are provided in [Table 4](#).

Subject-reported components of the CDAI (stool frequency and abdominal pain components and general well-being) will be collected in an electronic diary. Subjects will complete their electronic diary starting at Pre-baseline visit and will continue throughout the study.

Subjects will be instructed on the use and completion of questions on the electronic diary.

The diary entries will be reviewed by site personnel during pre-baseline and throughout the study.

Table 3: Crohn's Disease Activity Index Assessment

Clinical or Laboratory Variable	Weighting Factor, \times
Number of liquid or soft stools each day for 7 days	2
Abdominal pain (graded from 0-3 on severity) each day for 7 days	5
General well-being, assessed from 0 (well) to 4 (terrible) daily for 7 days	7
Presence of complications ^b	20
Taking diphenoxylate/atropine, loperamide, or opiates for diarrhea	30
Presence of an abdominal mass (0 as none, 2 as questionable, 5 as definite)	10
Hematocrit 47-HCT in men and 42-HCT in women	6
Percentage deviation from standard weight	1
Total Score	

Abbreviations: HCT = hematocrit.

^b One point each is added for each set of complications: arthritis or arthralgia; iritis or uveitis; erythema nodosum, pyoderma gangrenosum, aphthous stomatitis; anal fissure, fistula or perirectal abscess; other bowel-related fistula; febrile (fever) episode over 100 degrees during the past week.

Table 4: Crohn's Disease Severity Definitions

Severity	CDAI Score
Mild	150-219
Moderate	220-450
Severe	> 450

Abbreviations: CDAI = Crohn's Disease Activity Index.

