9.3 Sample Size and Power Considerations

As this is an Open-label Extension Study for subjects who participated in a prior study of ozanimod for CD, there is no statistical basis for the sample size. It is anticipated that approximately [REDACTED] subjects who participated in prior studies of ozanimod in CD will be eligible for treatment in this study.

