9.6 Efficacy Analysis

Due to the open-label nature of the study and the lack of a control group, all data will be summarized, and no hypothesis testing will be performed. Each efficacy endpoint will be summarized and [REDACTED] around the estimates may also be presented. All efficacy data will be listed.

For all proportion-based efficacy endpoints, subjects with missing efficacy data will be considered non-responders.

For continuous efficacy endpoints, subjects with missing data will have their last post-baseline value carried forward.

Observed-cases analyses will also be presented for all efficacy endpoints.

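### Section 9.6 states no rule for Crohn's surgery, so a subject who is operated on, resumes ozanimod and then meets a CDAI or symptom threshold counts as an ozanimod responder

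*Combined protocol and SAP*

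**What the plan says.** **Non-response.** For the responder endpoints, protocol Section 9.6 gives one rule: "For all proportion-based efficacy endpoints, subjects with missing efficacy data will be considered non-responders". For continuous endpoints the last post-baseline value is carried forward. It then adds: "Observed-cases analyses will also be presented for all efficacy endpoints". Neither the main nor the observed-cases analysis has a condition on surgery.

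**Endpoints.** Section 2.2.1 lists 13 efficacy endpoints. Eight are proportions that use CDAI or the abdominal pain and stool-frequency scores (three of them combined with SES-CD), and one is the change in CDAI. None mentions surgery. The only treatment condition is the requirement, in one endpoint, that the subject be off corticosteroids.

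**Surgery.** Section 8 requires that CD surgery be captured: "Additionally, all diagnostic, therapeutic, or surgical procedures relating to CD should be recorded". Section 8.1 treats surgery as a possible reason for a temporary break in dosing ("The decision to temporarily interrupt dosing for treatment of an intercurrent medical condition, or for major surgery that could present an unreasonable risk to the" participant) and refers to discussing re-initiation with the Medical Monitor. Surgery is not among the visible reasons for discontinuation in Sections 14.1 and 14.2.

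**Analysis set and baseline.** Section 9.2 includes every dosed subject. Section 9.4 fixes baseline at the last value before the first dose across the parent and extension studies, so a later operation does not reset it.

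**The concern.** An operation for Crohn's disease during treatment usually means that drug treatment alone did not control the disease. If the operation lowers the CDAI and the subject is back on ozanimod by the next annual visit, the rule in Section 9.6 credits the improvement to ozanimod. The surgical record that would identify the subject is collected but has no stated use in the efficacy analysis.

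The event is foreseeable. Section 4.2 admits subjects without response after induction and subjects who relapsed in maintenance, and treatment may last 264 weeks. The protocol's own background cites a study in which "within 10 years of diagnosis, 50% of adults with CD had undergone bowel surgery".

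No hypothesis is tested, so the yearly proportions are themselves the efficacy result. What is at stake is whether a year-5 remission rate can be read as remission on ozanimod, or as remission on ozanimod with or without an intervening bowel operation.

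**Working it through.** The plan gives no figure to reproduce. Section 9.6 says "no hypothesis testing will be performed", and Section 9.3 says "there is no statistical basis for the sample size". The check therefore has three parts.

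**1. Does the rule count such a subject?** Take a subject operated on for CD after the first dose in this study who restarts ozanimod and has a complete annual assessment with CDAI 120.
- The subject was dosed, so is in the analysis set (9.2).
- Data are not missing, so the non-response rule does not apply (9.6).
- 120 is below 150, so the CDAI remission endpoint is met, as is the endpoint of a 100-point fall or CDAI below 150.
- With a baseline at the lower end of the range in Section 9.1, the fall is 220 − 120 = 100 points, which also meets the 70-point endpoint.
- The pain/stool endpoint is not implied by the CDAI. It counts only if both scores meet their own limits.

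**2. Can surgery move the CDAI enough?** From Table 3 in Section 6.3.1:
- The stool item ("Number of liquid or soft stools each day for 7 days") has weight 2, so one stool per day is worth 2 × 7 = 14 points.
- A fall of 70/14 = 5 stools per day meets the 70-point endpoint alone. A fall of 100 points needs 100/14 ≈ 7.1 stools per day.
- Loss of a definite abdominal mass removes 5 × 10 = 50 points.
- Clearing one complication item, such as a fistula or abscess item, removes 1 × 20 = 20 points.

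An operation that changes these items can thus produce a CDAI response with no drug effect.

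**3. How large could the overstatement be?** Let *s* be the share of all dosed subjects who have CD surgery and resume ozanimod, and *r* the share of those who meet the threshold with non-missing data. The overstatement of the reported proportion is *s* × *r*. Neither value is in the documents; both ranges are assumptions.

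| *s* | *r* = 25% | *r* = 50% | *r* = 75% |
|---|---|---|---|
| 2% | 0.5 points | 1.0 | 1.5 |
| 5% | 1.25 | 2.5 | 3.75 |
| 10% | 2.5 | 5.0 | 7.5 |

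**CDAI change.** Under last observation carried forward, a low post-operative CDAI in a subject who later leaves is carried to every later year, so the mean change is affected in the same direction.

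**The case against.** The strongest objection is that much of the relevant text is unseen. Section 9 assigns detailed methods to the SAP, and an amendment summary says the CDAI calculation details moved there. The SAP text is not in the public document, Section 8.2 is absent, and Section 14.2 is shown only in part. A treatment-failure rule or a surgery-related discontinuation criterion may exist in one of them. This stands: a reader might infer that the trial has no rule at all, and the documents do not support that. They support only that Section 9.6 states none.

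Second, the affected group is narrow. Section 8.1 speaks of major surgery in general, not of resection for CD. Lack of efficacy is a listed reason to stop ozanimod, and a subject who stops for good and has no later data is already a non-responder. This also stands, but it limits the size of the problem and does not remove it: stopping for lack of efficacy is a decision of the subject or investigator, not automatic.

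Third, the study is uncontrolled and only explores efficacy, so no error rate is affected. True, but the descriptive rates are what will be reported.

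Fourth, permanent non-response is a debatable choice. A subject operated on in year 1 who does well on ozanimod for four more years would count as a failure throughout. That is a fair argument for showing both versions, not for leaving the choice unstated.

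A reader might also infer that a stoma meets the symptom endpoint by itself. The documents do not mention stomas or how stools are entered with one. If the diary item is left missing, the missing-data rule may already give non-response. Even a count of zero meets only the stool part, since pain must also be at most 1 and no worse than baseline.

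**Conclusion.** The point holds for the rule stated in Section 9.6. A subject who has a bowel resection or new stoma for CD after the first dose in this study, resumes ozanimod and meets a CDAI or pain/stool threshold with non-missing data is counted as an ozanimod responder. The direction of the bias is upward, and the number of subjects ever operated on grows with follow-up. The size is unknown; 0.5 to 7.5 percentage points is an illustration that rests wholly on the assumed 2% to 10% and 25% to 75%.

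Two stronger conclusions are tempting and not supported:
- A reader might turn the cited 50% within 10 years into a constant yearly rate (ln 2 / 10 = 0.0693, giving 1 − exp(−0.0693 × 5) = 29.3% by year 5) and infer a much larger bias. That figure runs from diagnosis and comes from population-based cohorts, not from entry into this extension. It gives neither the share who resume ozanimod nor the share who then meet a threshold. The main analysis also keeps dropouts in the denominator, which reduces the effect.
- A reader might extend the argument to corticosteroids started or raised for a flare. That depends on prohibited-medication text that is not visible, and one endpoint already requires CDAI below 150 off corticosteroids.

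**What to change.** Add to Section 9.6, and mirror in the SAP:

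- **Responder endpoints based on CDAI or on abdominal pain and stool frequency:** a subject is a non-responder at every annual visit on or after the date of a bowel resection or new stoma for CD that occurs after the first dose in this study.
- **Change in CDAI:** values after that date are not used in the main summary. The last pre-surgery value is carried forward under the existing rule.
- **Sensitivity:** keep the as-observed rates, with post-surgery values included.
- **Reporting:** give the number of subjects affected at each year, so that readers can judge the gap between the two versions.

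Confirm that the eCRF captures the date of each procedure; Section 8 requires the procedure to be recorded but does not say that its date is. If the SAP already holds an equivalent rule, a cross-reference in Section 9.6 is enough.

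The cost is a few sentences of analysis text and the date check. Reported late response rates become slightly lower, and subjects who do well on ozanimod after surgery count as responders only in the sensitivity summary. Nothing in the clinical management of subjects changes.

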8.1.1 Corticosteroid Taper

If subjects are still receiving corticosteroids in the Open-label Extension Study, subjects should begin tapering corticosteroids once clinical response or clinical remission has been achieved.

8.1.2 *Aminosalicylates or Purified Medicinal Probiotics*

Subjects receiving 5-aminosalicylic acid (ASA) or purified medicinal probiotics should maintain a stable dose throughout the study unless reduction or discontinuation is clinically indicated.

[figure not shown]
8.1.3 *COVID-19 Vaccination*

COVID-19 vaccines that are NOT live are allowed and should be handled in the same manner as other vaccines. Administration may occur during the study, including during treatment with IP and after the last dose of IP.

Non-live COVID-19 vaccination is considered a simple concomitant medication within the study. However, the efficacy and safety of non-live vaccines (including non-live COVID-19 vaccines) in subjects receiving ozanimod is unknown. The individual benefit/risk assessment of a vaccine remains with the Investigator. If the assessment of the Investigator suggests the vaccine to be beneficial, it must be a non-live, replication incompetent vaccine, and be approved or otherwise authorized (eg, Emergency Use Authorization [FDA] or equivalent) by national health authorities.

See [APPENDIX B](#) for further SARS-CoV-2 guidance.

